7.1.4 Methods for Evaluation of Measurable Disease

All measurements should be taken and recorded in metric notation using a ruler or calipers. All baseline evaluations should be performed as closely as possible to the beginning of treatment and never more than 4 weeks before the beginning of the treatment.

The same method of assessment and the same technique should be used to characterize each identified and reported lesion at baseline and during follow-up. Imaging-based evaluation is preferred to evaluation by clinical examination unless the lesion(s) being followed cannot be imaged but are assessable by clinical exam.

Clinical lesions: Clinical lesions will only be considered measurable when they are superficial (e.g. skin nodules and palpable lymph nodes) and 10 mm diameter as assessed using calipers (e.g. skin nodules). In the case of skin lesions, documentation by color photography, including a ruler to estimate the size of the lesion, is recommended.

Chest x-ray: Lesions on chest x-ray are acceptable as measurable lesions when they are clearly defined and surrounded by aerated lung. However, CT is preferable.

Conventional CT and MRI: This guideline has defined measurability of lesions on CT scan based on the assumption that CT slice thickness is 5 mm or less. If CT scans have slice thickness greater than 5 mm, the minimum size for a measurable lesion should be twice the slice thickness. MRI is also acceptable in certain situations (e.g. for body scans).

Use of MRI remains a complex issue. MRI has excellent contrast, spatial, and temporal resolution; however, there are many image acquisition variables involved in MRI, which greatly impact image quality, lesion conspicuity, and measurement. Furthermore, the availability of MRI is variable globally. As with CT, if an MRI is performed, the technical specifications of the scanning sequences used should be optimized for the evaluation of the type and site of disease. Furthermore, as with CT, the modality used at follow-up should be the same as was used at baseline and the lesions should be measured/assessed on the same pulse sequence. It is beyond the scope of the RECIST guidelines to prescribe specific MRI pulse sequence parameters for all scanners, body parts, and diseases. Ideally, the same type of scanner should be used and the image acquisition protocol should be followed as closely as possible to prior scans. Body scans should be performed with breath-hold scanning techniques, if possible.

Ultrasound: Ultrasound is not useful in assessment of lesion size and should not be used as a method of measurement. Ultrasound examinations cannot be reproduced in their entirety for independent review at a later date and, because they are operator dependent, it cannot be guaranteed that the same technique and measurements will be taken from one assessment to the next. If new lesions are identified by ultrasound in the course of the study, confirmation by CT or MRI is advised. If there is concern about radiation exposure at CT, MRI may be used instead of CT in selected instances.

Endoscopy, Laparoscopy: The utilization of these techniques for objective tumor evaluation is not advised. However, such techniques may be useful to confirm complete pathological response when biopsies are obtained or to determine relapse in trials where recurrence following complete response (CR) or surgical resection is an endpoint.

Tumor markers (*not applicable in this study*)

Cytology, Histology: These techniques can be used to differentiate between partial responses (PR) and complete responses (CR) in rare cases (e.g. residual lesions in tumor types, such as germ cell tumors, where known residual benign tumors can remain).

The cytological confirmation of the neoplastic origin of any effusion that appears or worsens during treatment when the measurable tumor has met criteria for response or stable disease is mandatory to differentiate between response or stable disease (an effusion may be a side effect of the treatment) and progressive disease.

7.1.5 Response Criteria

7.1.5.1 Evaluation of Target Lesions

Complete Response (CR): Disappearance of all target lesions. Any pathological lymph nodes (whether target or non-target) must have reduction in short axis to <10 mm.

Partial Response (PR): At least a 30 % decrease in the sum of the diameters of target lesions, taking as reference the baseline sum diameters.

Progressive Disease (PD): At least a 20 % increase in the sum of the diameters of target lesions, taking as reference the smallest sum on study (this includes the baseline sum if that is the smallest on study). In addition to the relative increase of 20 %, the sum must also demonstrate an absolute increase of at least 5 mm. (Note: the appearance of one or more new lesions is also considered progressions).

Stable Disease (SD): Neither sufficient shrinkage to qualify for PR nor sufficient increase to qualify for PD, taking as reference the smallest sum diameters while on study.

7.1.5.2 Evaluation of Non-Target Lesions

Complete Response (CR): Disappearance of all non-target lesions and normalization of tumor marker level. All lymph nodes must be non-pathological in size (<10 mm short axis).

Note: If tumor markers are initially above the upper normal limit, they must normalize for a patient to be considered in complete clinical response.

Non-CR/Non-PD: Persistence of one or more non-target lesion(s) and/or maintenance of tumor marker level above the normal limits.

Progressive Disease (PD): Appearance of one or more new lesions and/or unequivocal progression of existing non-target lesions. Unequivocal progression should not normally trump target lesion status. It must be representative of overall disease status change, not a single lesion increase.

Although a clear progression of “non-target” lesions only is exceptional, the opinion of the treating physician should prevail in such circumstances, and the progression status should be confirmed at a later time by the review panel (or Principal Investigator).

7.1.5.3 Evaluation of Best Overall Response

The best overall response is the best response recorded from the start of the treatment until disease progression/recurrence (taking as reference for progressive disease the smallest measurements recorded since the treatment started). The patient's best response assignment will depend on the achievement of both measurement and confirmation criteria.

Table 1: Response for patients with measurable disease (i.e., target disease)

Target Lesions	Non-Target Lesions	New Lesions	Overall Response	Best Overall Response when Confirmation is Required*
CR	CR	No	CR	≥4 wks. Confirmation**
CR	Non-CR/Non-PD	No	PR	≥4 wks. Confirmation**
CR	Not evaluated	No	PR	
PR	Non-CR/Non-PD/not evaluated	No	PR	
SD	Non-CR/Non-PD/not evaluated	No	SD	documented at least once ≥4 wks. from baseline**
PD	Any	Yes or No	PD	no prior SD, PR or CR
Any	PD***	Yes or No	PD	
Any	Any	Yes	PD	

* See RECIST 1.1 manuscript for further details on what is evidence of a new lesion.

** Only for non-randomized trials with response as primary endpoint.

*** In exceptional circumstances, unequivocal progression in non-target lesions may be accepted as disease progression.

Note: Patients with a global deterioration of health status requiring discontinuation of treatment without objective evidence of disease progression at that time should be reported as “*symptomatic deterioration*”. Every effort should be made to document the objective progression even after discontinuation of treatment.

Table 2: Tumor response for patients with non-measurable disease (i.e., non-target disease)

Non-Target Lesions	New Lesions	Overall Response
CR	No	CR
Non-CR/non-PD	No	Non-CR/non-PD*
Not all evaluated	No	not evaluated
Unequivocal PD	Yes or No	PD
Any	Yes	PD

* 'Non-CR/non-PD' is preferred over 'stable disease' for non-target disease since SD is increasingly used as an endpoint for assessment of efficacy in some trials so to assign this category when no lesions can be measured is not advised.

7.1.6 Duration of Response

Duration of overall response: The duration of overall response is measured from the time measurement criteria are met for CR or PR (whichever is first recorded) until the first date that recurrent or progressive disease is objectively documented (taking as reference for progressive disease the smallest measurements recorded since the treatment started).

The duration of overall CR is measured from the time measurement criteria are first met for CR until the first date that progressive disease is objectively documented.

Duration of stable disease: Stable disease is measured from the start of the treatment until the criteria for progression are met, taking as reference the smallest measurements recorded since the treatment started, including the baseline measurements.

7.1.7 Progression-Free Survival (PFS)

PFS is defined as the time elapsed from randomization to the date of documented progression or death, whichever comes first. For surviving patients without progression who begin alternative treatment, PFS will be censored at the last date of documented progression-free status prior to starting alternative treatment. Similarly, losses to follow up will be censored at the last date of documented progression-free status.

7.1.8 Overall response rate (ORR)

ORR i.e. overall response rate is defined as the sum of the complete and partial response rate as detailed in [Section 7.1.5](#).

7.1.9 Overall Clinical benefit rate (CBR)

CBR is defined as the sum of the complete response and partial response and stable disease rate as detailed in [Section 7.1.5](#).

Additionally, we define clinical benefit as non-progression at 9 weeks with no toxicity requiring termination of treatment.

7.1.10 Overall survival

Overall survival (OS) is defined as the elapsed time from randomization to death from any cause. For surviving patients, follow-up will be censored at the date of last contact.

7.2 Safety

7.2.1 Adverse events

7.2.1.1 Definitions

An adverse event (AE) is any untoward medical occurrence in a patient or clinical investigation subject administered a pharmaceutical product and which does not necessarily have a causal relationship with this treatment. An adverse event (AE) can therefore be any unfavorable and unintended sign including an abnormal laboratory (or vital, ECG etc.) finding^A, symptom or disease^B temporally associated with the use of a medicinal (investigational) product, whether or not considered related to the medicinal (investigational) product.

A Documentation rules for abnormalities in laboratory finding, vital signs, ECG etc. are specified in [Section 7.2.1.3](#).

B This will also include intercurrent diseases and accidents observed during treatment period as well as corresponding events during drug-free periods, under placebo or in a reference group receiving drug or non- drug therapy.

Serious adverse event (SAE) means any untoward medical occurrence that at any dose^A:

- results in death,
- is life-threatening^B,
- requires inpatient hospitalization or prolongation of existing hospitalization^C,
- results in persistent or significant disability or incapacity,
- is a congenital anomaly / birth defect or
- is another medically important condition^D.

^A All events that meet the definition of an SAE but, in the opinion of the treating investigator, are clearly expected from the patient's disease or related to disease progression (i.e., there exists no reasonable possibility that they were caused by the study drug) should be recorded on the case report forms only and do **not** require the reporting as an SAE (as defined in protocol [Section 7.2.1.4](#)). This will also apply to patient's death that is clearly attributed to the underlying malignant disease.

^B The term "life-threatening" in the definition of "serious" refers to an event in which the patient is at risk of death at the time of the event; it does not refer to an event that hypothetically might have caused death if it were more severe.

- C. Hospitalization for elective treatment of a pre-existing condition that did not worsen during the clinical investigation is not considered an AE. Admittance to an emergency room for observation without being admitted to the hospital may be considered an AE, but is not considered as an SAE. Hospitalization or nursing home admission for the purpose of caregiver respite is not considered an AE. Hospitalizations for symptoms of progressive disease are not considered an SAE. Complications that occur during hospitalization are AEs, and if a complication prolongs hospitalization, the event is considered serious.
- D. Medically important conditions that may not result in death, be life threatening or require hospitalization may be considered as SAE when, based upon appropriate medical judgment, they may jeopardize the patient or may require intervention to prevent one of the outcomes listed in the definition above. Examples of such events are intensive treatment in an emergency room or at home for allergic bronchospasm; blood dyscrasias or convulsions that do not result in hospitalization; or development of drug dependency or drug abuse [Ref: Federal Register §312.32 IND safety reports].

Please note: The term “severe” is often used to describe the intensity (severity) of an event (as in mild, moderate, or severe pain); the event itself may be of relatively minor medical significance (such as severe headache). This is not the same as “serious”, which is based on patient/event outcome or action criteria usually associated with events that pose a threat to patient's life or vital functioning. Seriousness (not severity) serves as a guide for defining regulatory reporting obligations.

Severity Grading

The NCI Common Terminology Criteria for Adverse Events (version 4.03 or subsequent ones) are to be used for the grading of severity of symptoms and abnormal findings. A copy of the document is included in the investigator's file (see also: <http://evs.nci.nih.gov/ftp1/CTCAE/About.html>).

For adverse events not covered by the NCI-CTCAE grading system, the following definitions will be used:

- **Grade 1 - Mild:** awareness of sign, symptom, or event, but easily tolerated
- **Grade 2 - Moderate:** discomfort enough to cause interference usual activity and may warrant intervention
- **Grade 3 - Severe:** incapacitating with inability to do usual activities or significantly affects clinical status, and warrants intervention
- **Grade 4 - Life-threatening:** immediate risk of death (Note: will require reporting as an SAE)

Causality assessment

The investigator will assess the causal relationship of an AE/SAE to the study drug using the following categories and definitions.

- **Likely** (at least 3 of the following conditions must apply):
 - AE had a reasonable temporal relationship to administration of trial medication;
 - AE could not readily have been produced by the subject's clinical state or have been due to environmental or other interventions;
 - AE followed a known pattern of response to the trial medication;
 - AE disappeared or decreased with reduction in dose or cessation of the trial medication.
- **Possible** (at least 2 of the following conditions must apply):
 - AE had a reasonable temporal relationship to administration of trial medication;
 - AE could not readily have been produced by the subject's clinical state;
 - AE could not readily have been due to environmental or other interventions;
 - AE followed a known pattern of response to the trial medication.
- **Unlikely** (at least 2 of the following conditions must apply):
 - AE did not have temporal relationship to administration of trial medication;
 - AE could readily have been produced by the subject's clinical state;
 - AE could have been due to environmental or other interventions;
 - AE did not follow known pattern of response to the trial medication;
 - AE did not reappear or worsen with reintroduction of the trial medication.
- **Unrelated:**
 - AE was clearly due to extraneous causes (e.g. underlying disease, environment).

7.2.1.2 Procedures in case of adverse events

Throughout the study, the patient will be questioned and/or examined by the Investigator or his/her designee for evidence of adverse events. The questioning of patients with regard to the possible occurrence of adverse events should be as non-specific as possible.

However, given that it is the site's responsibility to follow up all AEs, specific questions related to previously reported AEs with regard to their resolution or continuation must be asked.

All adverse events occurring during a study have to be documented, regardless of any assumption of a causal relationship, on the respective AE CRF. All events that occurred during the screening period should be documented as medical history. The investigator should ensure, e.g. by telephone call to the trial subject, to record all events that occurred within 28 days after the last exposure to study drug.

Documentation of adverse events includes date of onset and offset, pattern, duration, severity, impact, actions taken, seriousness, and outcome. The investigator should also

evaluate the probability of a causal relationship of the adverse event to the study medication as likely, possible, unlikely, or unrelated. Information provided in the Investigator's Brochure may support this evaluation.

7.2.1.3 Documentation of routine safety parameters

A value outside the normal or reference range in a routine safety assessment, such as clinical laboratory, vital signs, or ECG, may signify an adverse finding. If the investigator considers the abnormality as clinically significant/relevant, as defined below, he should also record this on the CRF Adverse Events [Note: A clinically significant abnormality observed prior to first administration of study treatment should be recorded as update of the CRF Medical History]. If the findings contribute to a clinical diagnosis, such as hepatitis in case of increased liver enzymes, this diagnosis should be recorded as adverse event.

An abnormality must be considered as clinically significant, if

- it represents a serious adverse event, or
- it led to premature discontinuation of the study, or
- it required a therapeutic measure, or
- in the judgment of the investigator - it indicates a medically relevant condition or risk, without meeting any of the above criteria.

7.2.1.4 Reporting of serious adverse event

The investigator must report serious adverse events (SAE) occurring or observed from the day of first administration of the investigational drug on and until 4 weeks after last administration of the investigational drug (development of impaired cardiac function (ex. \geq grade 4 left ventricular systolic dysfunction) within 1 year after last administration of study drug should also be reported as an SAE); see page 2 for contact persons and email/phone/fax numbers. As soon as possible, but in no case later than 24 hours after the SAE has been noted, the "Serious Adverse Event Report" form (*copies included in the Investigator's File*) should be sent by email, whether or not complete information is available within this period. In case of incomplete information, the investigator has to provide follow-up information as soon as possible, again using the SAE report form.

Regarding hospitalization, please refer to [Section 7.2.1.1](#), footnotes A and C for circumstances that will determine the consideration as SAE and need for reporting on an SAE form to AEZS drug safety.

All events that meet the definition of serious but, in the opinion of the treating investigator, are clearly expected from the patient's disease or related to disease progression (i.e., there exists no reasonable possibility that they were caused by the study drug) should be reported on the case report forms and do not require immediate reporting on an SAE form.

This will also apply to patient's death that is clearly attributed to the underlying malignant disease.

Reports will be evaluated by Aeterna Zentaris and authorities will be informed according to national or international regulations. The same information will also be made available to principal investigators of other currently ongoing trials with the same study medication.

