6 DESCRIPTION OF TREATMENTS

Subject will be randomly allocated to receive either:

- AEZS-108 - Investigational drug (Arm A)
- OR
- Doxorubicin – Comparator drug (Arm B).

Details related to AEZS-108 (Arm A) are presented in [Section 6.1](#) while those related to doxorubicin (Arm B) are provided in [Section 6.2](#). Information provided in [Section 6.3](#) to [Section 6.4](#) is applicable to both, Arm A and Arm B.

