6.1.3 Treatment modifications / delay of treatment

Any deviation from the planned dosing schedule must be commented on in the CRFs.

Delay of re-treatment: Subsequent cycles of study treatment should not begin before a patient has recovered to CTCAE Grade 1 from a drug-related adverse event (i.e., causality at least possibly related) that the investigator feels is clinically significant. No treatment delay is required for alopecia or anemia for which supportive therapy should be given according to study sites' clinical practice (see also 6.3.1.3). Re-treatment may be postponed for up to 2 weeks. A patient who has not recovered within 5 weeks after the last dose should be withdrawn and followed up as required.

Dose reduction: Any of the following drug-related adverse events (i.e., causality at least possibly related) will require a dose modification, if its duration exceeds the indicated period:

- Grade 4 neutropenia [ANC < 500/mm³] lasting 7 days or more

- Grade 3 febrile neutropenia lasting for more than 7 days
[Grade 3 defined as: ANC < 1000/mm³ with a single temperature of >38.3 °C (101 °F) or a sustained temperature of ≥ 38 °C (100.4 °F) for more than one hour]
- Grade 4 febrile neutropenia (of any duration)
[Grade 4 defined as: Life-threatening consequences; urgent intervention indicated]
- Grade 3 thrombocytopenia [Platelet count: < 50,000 – 25,000/mm³] persistent at the scheduled time of re-dosing (i.e. blood sample on the day before re-dosing) and associated with a clinical risk of bleeding (presenting, e.g. as hemorrhagic diathesis: petechial rash, especially affecting tunica mucosa in oral cavity, gingival rash or petechial skin rash associated with prolonged bleeding time, e.g. in the Duke bleeding time test)
- Any other Grade 4 hematological toxicity (except for lymphocytopenia) lasting 7 days or more
- Grade 3 nausea/vomiting/diarrhea lasting 5 days or more despite optimal medical management.

If any of the above dose-limiting toxicities occurs and re-treatment is indicated after the toxicity has resolved to ≤ Grade 1 within the allowed period for a treatment delay, then dosing will be resumed with a dose reduction.

Dose Level	AEZS-108 Dose (mg/m ²)
Starting Dose	267
1 st Dose Reduction (approximate 20 % reduction)	210
2 nd Dose Reduction (approximate 40 % reduction)	160

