8.4 Procedures during treatment

8.4.1 Procedures on Cycle 1 Day 1 (date of first study treatment)

After randomization, but prior to first administration of study treatment, each patient will have the following assessments and tests:

- **Interval history** and symptom-directed examination
Findings to be recorded as Medical History / Concomitant Disease/Condition
- **Clinical assessments** (including ECOG performance status, blood pressure, pulse, and weight for BSA and dose calculation)
- **Clinical laboratory** tests (hematology, chemistries, urinalysis)
- **Eligibility criteria review**
In the absence of new findings that would violate any of the eligibility criteria,

except for Day 1 clinical laboratory tests, the patient may receive the allocated study treatment.

- **Study treatment**
Administration of allocated study medication at the recommended starting dose.
- **Sparse PK sampling (AEZS-108 treated patients only)**
Blood collections within the following time windows:
sample #1: within 60 minutes before end of the 2-hour infusion
sample #2: between 30 and 60 minutes after the end of infusion (EOI)
sample #3: between 120 and 180 minutes after EOI;
sample #4 (optional): between 4 and 6 hours after EOI.

A patient, in whom sparse PK sampling was not possible in Cycle 1, may have the samples taken at any subsequent cycle. It is not planned to have repetitive sparse sampling of the same patient during multiple cycles.
- **PK substudy (instead of ‘sparse PK sampling’, at selected investigational sites only)**
Procedures related to the PK substudy are described in Appendix 7 of the protocol.

8.4.2 Weekly procedures during Cycle 1

Once weekly controls during Cycle 1 will include the following:

- **Clinical assessments** (including blood pressure and pulse)
- **Clinical laboratory tests** (hematology, chemistries, urinalysis)
- **Adverse event** recording.

Retreatment is planned in 3-weekly intervals, i.e. Day 1 of new cycle is corresponding to Day 22 of the previous cycle. In case of incomplete recovery from hematological toxicity or adverse events, re-treatment may be delayed for up to 2 weeks, i.e. with appropriate supplementary weekly controls on Day 29 and Day 35 (see [Section 6.1.3](#)).

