8.5 Procedures at end of study treatment

A patient who is going off study treatment (see [Section 5.3](#)) – will have the assessments/investigations specified below.

As an end-of-cycle assessment, it should be scheduled 3 to 5 weeks (Day 21 to 35) after the last dose. Additional visits/assessments may be indicated to follow-up unresolved adverse events.

- **Interval history** and symptom-directed examination
- **Clinical laboratory** tests (hematology, chemistries, urinalysis, hormones)
- **Cardiac function:**
 - 12-lead electrocardiogram (ECG)
 - Left ventricular ejection fraction (LVEF): Echocardiogram or MUGA
- **Quality of Life:** questionnaires
- **Tumor imaging (CT or MRI):** evaluation of time-point response by comparison with target and non-target lesions defined at screening (baseline)
- **Final evaluations:** best response, reason for discontinuation, investigator's overall judgment on tolerability of study treatment

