9.6.1 Adverse events

Each AE and SAE term reported will be mapped to a preferred term (PT) using the MedDRA dictionary. The investigator will classify the severity of AEs using the NCI CTCAE v4.03 and will assess the relationship of each event to study treatment.

All AEs and SAEs occurring on study will be listed by patient. The frequency and percentages of patients with treatment-emergent adverse events (TEAEs) will be tabulated by system organ class (SOC) and PT, where treatment-emergent is defined as any AE that:

- Occurs after randomization and through the follow-up of the last treatment cycle or, if an SAE, until the event has resolved or stabilized,
- Is considered treatment-related regardless of the start date of the event, or
- Is present before randomization but worsens in intensity.

TEAEs that are considered at least possibly related to study treatment will be tabulated as well as deaths, SAEs, and events resulting in treatment discontinuation.

At each level of summarization, a patient will be counted only once for each AE, SOC, or PT experienced within that level. In the summation for AE severity, within each level of AE, SOC, or PT experienced, the one with the highest severity will be included. In the summation for AE's relationship to the study drug, within each level of AE, SOC, or PT experienced, the one with the closest relationship to the study drug will be included.

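### Non-cardiac SAEs that first arise on Days 29-35 after the final dose need no expedited report, although the end-of-therapy visit and the recovery period run to Day 35

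*Protocol*

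**What the plan says.** **SAE reporting.** Protocol Section 7.2.1.4 covers SAEs "occurring or observed from the day of first administration of the investigational drug" and "until 4 weeks after last administration of the investigational drug", with a form due within 24 hours. There is one extension: impaired cardiac function "within 1 year after last administration of study drug should also be reported as an SAE". Serious events that the investigator clearly attributes to the cancer go on the CRF only.

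**AE recording.** Protocol Section 7.2.1.2 requires all adverse events during the study to be documented. It asks the investigator to make sure, for example by telephone, that events within 28 days of last exposure are captured.

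**End of therapy.** Of the end-of-therapy assessment, Protocol Section 8.5 says "it should be scheduled 3 to 5 weeks (Day 21 to 35) after the last dose".

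**Recovery period.** Protocol Section 6.1.3 states: "A patient who has not recovered within 5 weeks after the last dose should be withdrawn and followed up as required". Section 6.2.3 has the same rule for doxorubicin, and note 3 of the Flow Chart repeats the 5-week limit for both arms. Section 8.4.2, for Cycle 1, provides for delayed re-treatment "with appropriate supplementary weekly controls on Day 29 and Day 35".

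**Analysis windows.** The first limb of the treatment-emergent definition in Protocol Section 9.6.1 reads "Occurs after randomization and through the follow-up of the last treatment cycle", extended for an SAE until it resolves or stabilizes. SAP Section 9.1 uses the end of the study or 30 days after the last dose. Both sections also count any treatment-related event whatever its start date.

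**The concern.** The duty to report SAEs stops up to a week before the protocol stops looking at the patient for toxicity. A patient who has not recovered can be held until Day 35 and then withdrawn, and her end-of-therapy visit can fall on the same day. If a new serious event starts in that last week and no further dose follows, the site finds it at a scheduled contact but has no duty to send the 24-hour form, even if it judges the event related.

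The rule is also awkward to apply in real time. On Day 30 a site may not know whether the patient will be re-dosed, and re-dosing decides whether Day 30 lies inside the window.

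The protocol accepts for cardiac function that 4 weeks can be too short, but has no matching clause for other related serious events. At stake is the timeliness of safety information to the sponsor, the DSMB and the authorities. In an open-label trial, voluntary late reporting could also differ between arms.

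**Working it through.** **1. Day arithmetic (days after the last dose)**

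| Item | Source | Calculation | Day |
|---|---|---|---|
| SAE window closes | Protocol 7.2.1.4 | 4 × 7 | 28 |
| Active AE recording | Protocol 7.2.1.2 | stated | 28 |
| End-of-therapy visit | Protocol 8.5 | 3 × 7 to 5 × 7 | 21 to 35 |
| Recovery limit | Protocol 6.1.3, 6.2.3 | (3 + 2) × 7 | 35 |
| TEAE limit, second alternative | SAP 9.1 | stated | 30 |

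The protocol's own Day 21 to 35 is reproduced.

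- Gap: 35 − 28 = 7 days. If the general ±3-day visit window in the Flow Chart is added, 38 − 28 = 10 days.
- Permitted visit days: 35 − 21 + 1 = 15. Days 21-28 (8 days) are inside the SAE window and Days 29-35 (7 days) are after it.
- The SAP's 30-day limit exceeds the SAE window by 30 − 28 = 2 days.

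**2. Which events are exposed**

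An event falls in the gap only if all of these hold:

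- It first occurs, or first becomes serious, on Days 29-35. An event occurring or observed as serious by Day 28 is reportable, and missing information must be supplied later.
- No further dose is given. Re-dosing restarts the clock.
- It is not impaired cardiac function, which has its own one-year window.
- It is not clearly attributed to the cancer.

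No text in either document extends general SAE reporting past Day 28.

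**3. Rough size**

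Inputs, all from Protocol Section 1.2.2:

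- In the Phase II endometrial study, 13 of 43 patients had an SAE other than death, and 6 of 43 had a related SAE.
- Hematotoxicity delayed re-treatment in fewer than 10% of patients. In the endometrial study, leukopenia delayed dosing by 7 days or more in about 5%.

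Assumptions: a constant rate over 18 to 27 weeks (6 to 9 cycles of 3 weeks), carried unchanged into the fifth week after the last dose, and equal in both arms.

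Weekly rate = −ln(1 − p) / weeks.

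- All-cause SAE: −ln(30/43) = 0.360. Divided by 27 and by 18, this is 0.0133 to 0.0200 per patient-week.
- Related SAE: −ln(37/43) = 0.150. Divided by 27 and by 18, this is 0.0056 to 0.0083 per patient-week.

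Expected first events in one week (Days 29-35):

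- Delayed-recovery group, 5-10% of 500 = 25 to 50 patients, all-cause rate: 25 × 0.0133 = 0.33 to 50 × 0.0200 = 1.0.
- All 500 patients, related rate: 500 × 0.0056 = 2.8 to 500 × 0.0083 = 4.2, or about 3-4.

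**The case against.** The strongest defense is that an expedited form is not the same as data capture. Section 7.2.1.2 wants all adverse events during the study on the CRF, with seriousness. The Flow Chart has cumulative recording, its note 7 follows drug-related events that ended treatment to outcome, and Section 8.5 allows extra visits for unresolved events. The SAP tabulates from the CRF, and both TEAE definitions take in related events whatever their start date. A reader might infer that the gap removes events from the serious-TEAE comparison. The documents do not support that: a related sepsis on Day 32 counts as a serious TEAE once it is on the CRF. This part of the defense stands.

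Three other stronger readings also fail.

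- *Serious events in non-recovering patients are unreported as a class.* They are not. Events serious by Day 28 are covered, re-dosing moves the window, and 8 of the 15 permitted visit days lie inside it.
- *Arm B has no SAE window.* Section 6 labels only "AEZS-108 - Investigational drug (Arm A" as investigational and calls doxorubicin the comparator. But the cardiac clause in the same sentence of Section 7.2.1.4 refers to study drug, Sections 7.2.1.1 and 7.2.1.2 do likewise, and the safety population covers both arms. In context the duty applies to both. The term should be tidied, but no arm is uncovered.
- *The Phase II all-cause SAE rate over all 500 patients, or the deaths expected in a week, measures the loss.* Neither does. The all-cause proportion may include events exempt as disease-related and does not isolate delayed recovery. Deaths clearly due to the cancer are exempt at any time, and every death is sought for the primary endpoint.

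The Day 35 control should not be pressed either. It appears under Cycle 1 procedures, and the Flow Chart lists only Day 22 and Day 29.

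Finally, 4 weeks can be defended as a choice. It matches the 28-day AE rule, exceeds the 21-day cycle, and spans 28 × 24 / 48 = 14 half-lives at the upper end of the 20 to 48 hour range for doxorubicin in Appendix 7, Section 1.3. In Phase II, neutropenia of grade 3 or higher was seen only on Day 15. This supports a low event count in week 5. It does not explain why a related serious event found at a protocol visit should be exempt from prompt reporting.

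**Conclusion.** The gap is real and narrow. It follows from a stated rule, not from missing detail. The certain loss is the 24-hour report, and loss from the safety tables is not shown.

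The likely number is small: about 0.3-1 SAE in the delayed-recovery group, or about 3-4 related first SAEs across all 500 patients. These are orders of magnitude only. They rest on 43 Phase II patients treated with AEZS-108, a rate held constant into week 5, and the assumption that doxorubicin behaves alike. The true rate after treatment could well be lower.

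A second, related finding is that the windows do not agree. Active AE recording and SAE reporting end at 28 days, the protocol's TEAE definition runs through follow-up of the last cycle or to SAE resolution, and the SAP offers two alternative end points. These should be reconciled whatever length the sponsor prefers. Overall this is a cheap improvement to safety reporting and does not threaten the trial's conclusions.

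**What to change.** In Protocol Section 7.2.1.4:

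- Start SAE reporting at the first dose of study treatment, naming both AEZS-108 and doxorubicin. This clarifies the wording and does not change the scope.
- End it at the later of 4 weeks after the last dose and the End-of-Therapy assessment.
- After that, require a report of any SAE considered at least possibly related, whenever it is noted. Keep the one-year cardiac clause.

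Then bring Protocol Sections 7.2.1.2 and 9.6.1 and SAP Section 9.1 to the same end point, and remove the SAP's choice between end of study and 30 days.

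The cost is a short protocol amendment, matching SAP wording and a few more SAE forms. No visit or procedure is added, and no dosing or treatment-delay rule is touched. Because the end-of-therapy day varies, the window would differ by up to a week between patients, so the timing of that visit should be summarized by arm.
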